9.3. Prohibitions and Restrictions in the Study

9.3.1. Medication

During the entire duration of the study (from Screening visit to EOS/ET visit) use of following medications, treatment modalities, or diets are prohibited:

- a. Use of drugs for weight loss e.g. Orlistat (Xenical), Naltrexone HCl/Bupropion HCl (Contrave), etc.,
- b. Use of anticoagulant/antiplatelet therapy or medications or dietary supplements which impede coagulation or platelet aggregation,
- c. Any cosmetic or interventional surgery procedures on area to be treated,
- d. Use of terfenadine (Teldane), buspirone (Buspar), fexofenadine (Fexotabs, Tefodine, Telfast, Xergic, Allegra, etc.), any medication that is known to strongly inhibit or induce CYP enzymes (please refer to Section 24.1), sensitive CYP substrates or drugs with narrow therapeutic index, in the opinion of the investigator, may affect the evaluation of the study product or place the participant at undue risk,

If a subject needs to use the above mentioned therapeutic agents during the study for any reason, these therapeutic agents should not be used at least for 2 days prior to dosing and until 1 day post-dose,

- e. Use of other investigational drug or device within 4 weeks prior to Screening.
- f. Use of medication which is delivered via subcutaneous injection at the treatment area during the study period.

Subjects should be advised not to take any prescription and OTC medications without consulting the Investigator.

9.3.2. Contraception

Highly effective contraceptive methods that can achieve a failure rate of less than 1% per year when used consistently and correctly should be used. The list below is based on the recommendation of the Clinical Trial Facilitation Group (CTFG 2014).

- combined (estrogen and progestogen containing) hormonal contraception associated with inhibition of ovulation:
 - oral
 - intravaginal
 - transdermal
- progestogen-only hormonal contraception associated with inhibition of ovulation¹:
 - oral
 - injectable
 - implantable¹
- intrauterine device (IUD)¹
- intrauterine hormone-releasing system (IUS)¹
- bilateral tubal occlusion¹
- vasectomized partner^{1,2}
- sexual abstinence³
- condom used by male partner during sexual intercourse.

Contraceptive requirements for male subjects with WOCBP partner: A male subject should use condom during heterosexual intercourse and avoid sperm donation from the time of the first dose of study drug, throughout study participation until 12 weeks after the last study drug dose. For the WOCBP partner, contraception recommendations should also be considered.

¹ Contraception methods that in the context of this guidance are considered to have low user dependency.

² Vasectomized partner is a highly effective birth control method provided that partner is the sole sexual partner of the WOCBP trial participant and that the vasectomized partner has received medical assessment of the surgical success.

³ In the context of this guidance, sexual abstinence is considered a highly effective method only if defined as refraining from heterosexual intercourse during the entire period of risk associated with the study treatments. The reliability of sexual abstinence needs to be evaluated in relation to the duration of the clinical trial and the preferred and usual lifestyle of the subject. Periodic abstinence (calendar, symptothermal, post-ovulation methods) and

withdrawal (coitus interruptus) are not acceptable methods of contraception. This is applicable for both female and male subjects.

9.4. Screen Failures

Screen failures are defined as subjects who consent to participate in the clinical study but are not subsequently enrolled in the study. A minimal set of screen failure information is required to ensure transparent reporting of screen failure subjects to meet the Consolidated Standards of Reporting Trials publishing requirements and to respond to queries from regulatory authorities. Minimal information includes screen failure details, eligibility criteria, and any SAE. Individuals who do not meet the criteria for participation in this study (screen failure) may be re-screened. Re-screening will be allowed once within the recruitment period for the study. Re-screened participants should be assigned a new screening number.

9.5. Subject Replacement

Subjects who are enrolled but who do not receive any IP will be replaced and the replacement subject will receive the same treatment as the subject they are replacing. Subjects who discontinue the study prior to completion of dosing may be replaced at the discretion of the Sponsor.

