10.4. Method of Assigning Participants to Treatment

10.4.1. Randomization

Sponsor or designee will manage the randomization of eligible study participants in the study. The randomization schedule will be generated before the start of dosing.

Each subject will be provided with a unique screening number post-documentation of informed consent. Subjects who withdraw from the study, for any reason, without completing all necessary screening assessments will be considered screen failures (see Section 9.4).

Stage 1 of the study will be open label with a total 24 subjects sequentially enrolled in 4 dose groups (6 subjects in each group) to receive one course of allocated CBL-514 dose as presented in Table 7. Once deemed eligible for enrolment in the study, each subject will be assigned a sequential subject number prior to first dosing.

Stage 2 of the study will be a randomized, single-blind, parallel-group. Considering drop-out rates (16% CBL-514 group vs 44% placebo group), approximately 75 subjects are planned to be enrolled and randomized 2:1 (50 subjects in the CBL-514 group and 25 subjects in the placebo group) in order to have a total of at least 56 evaluable subjects in Stage 2 of the study. The dose of CBL-514 used in Stage 2 will be set no higher than the highest safe dose from Stage 1. Once deemed eligible for enrolment in the study, each subject will be assigned a sequential randomization number prior to first dosing.

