10.7. Blinding

Stage 2 of this study will be conducted in a single-blind manner where the subjects are blinded to treatment but the Investigator, site staff, and the Sponsor, including the Medical Monitor, will be unblinded to treatment assignment to assess safety on an ongoing basis.

Methods of blinding

- Due to the difference in appearance of the placebo and CBL-514, to keep the study single blind, the study needs to create visual barriers to blind subjects. Blinding for subjects will be maintained by physical barrier "sheet" placed over the chest obstructing the subjects own view of their abdomen, using a blindfold/sunglasses to cover subjects' eyes while administration takes place.

If during the study the blind is broken for any reason:

- The reason for unblinding is to be documented in the subject's source documents and case report forms (CRFs). Subjects that were unblinded for any reason during their participation in the study will not be replaced.
- As soon as possible, and without revealing the subject's study treatment assignment (unless important to the safety of participants remaining in the study), the Investigator must notify the Sponsor about unblinding and the reason for unblinding.

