12.2.2. Visit 2: Treatment/Baseline (Day 1)

12.2.2.1. Before Dosing

Prior to dosing on Day 1, subjects will be randomized to respective groups (i.e., CBL-514 group or placebo group) after confirmation of eligibility.

The following assessments will be carried out prior to the administration of IP unless otherwise noted³:

- Determine subject's eligibility based on inclusion/exclusion criteria
- Collect anthropometric parameters (including body weight)
- Perform abdominal ultrasound. Abdominal ultrasound may be performed up to 4 days before Day 1
- Perform medical examinations:
 - Physical examination⁴
 - Injection site assessment
 - Vital signs (body temperature, pulse rate, systolic and diastolic BP, and respiratory rate) evaluation⁴
 - ECG⁴
- Collect blood/urine to perform laboratory evaluations⁴:
 - Biochemistry panel
 - Hematology panel
 - Coagulation panel
 - Urinalysis
 - Pregnancy test for WOCBP (urine)
- Randomization
- Take photographs on the target abdominal area pre-dose.
- Before the administration of the injections,
 - Subjects will take an analgesic (pain killer) as recommended by the Investigator
 - Wipe subject's abdomen with an antiseptic solution
 - Apply local anesthesia used in local practice to the injection area

³ Available measurements of clinical evaluations (physical examinations, vital signs, and ECG) and laboratory evaluations (biochemistry, hematology, coagulation, and urinalysis) **within 14 days prior to CBL-514/Placebo dose** can be accepted as the Baseline value and will not necessitate duplicate examinations. If study drug dose is within 7 days of Screening pregnancy test, pregnancy test on Day 1 will not necessitate be necessary to assess.

In cases where more than 1 data is available for a certain evaluation, the latest value prior to the study drug administration will be used as the Baseline value.

⁴ Assessment/collection can be performed on or within 4-days window prior to visit date.

- A cold compress may also be applied before the injection(s) if needed

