4.1 Population Descriptions

4.1.1 Intent-to-treat (ITT Population)

All assigned or randomized subjects, regardless of whether they receive treatment or not, will be included in the ITT population. Summaries, listings, and analyses by treatment group will be based on the subject's randomly assigned treatment, not what they actually received.

All demographic data analysis will be based on the ITT population. All listings will be presented by the ITT population.

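### Protocol 9.5 is not limited to Stage 1, so a Stage 2 replacement for a randomised but never-dosed subject has an arm fixed by rule and knowable in advance, not drawn at random

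*Protocol*

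**What the plan says.** Protocol 9.5 contains two replacement rules, and neither names a stage.

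- **Never dosed (mandatory):** an enrolled subject who is given no product must be replaced, and "the replacement subject will receive the same treatment as the subject they are replacing".
- **Stopped during dosing (optional):** "Subjects who discontinue the study prior to completion of dosing may be replaced at the discretion of the Sponsor". Nothing is said about the arm of this replacement.

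The provisions that govern Stage 2 are these.

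- Protocol 12.2.2.1: "Prior to dosing on Day 1, subjects will be randomized to respective groups".
- Protocol 10.4.1: "Sponsor or designee will manage the randomization of eligible study participants in the study", and "each subject will be assigned a sequential randomization number prior to first dosing". It describes no reserved replacement numbers and no concealment procedure.
- Protocol 10.3.2 has all Stage 2 enrollees randomised 2:1 and makes no exception for replacements. Footnote 17 of Table 5 likewise provides for random assignment.
- Protocol 10.7: "the Investigator, site staff, and the Sponsor, including the Medical Monitor, will be unblinded to treatment assignment". Only subjects are blinded. The one stated bar on replacement concerns subjects whose blind has been broken.
- SAP 4.1.1: "All assigned or randomized subjects, regardless of whether they receive treatment or not, will be included in the ITT population", grouped by random assignment. Protocol 16.1.1 instead requires at least one course of product. Neither definition separates replacements.
- Protocol 16.3.2 makes ITT the analysis set for the Stage 2 primary endpoint.

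**The concern.** A same-treatment replacement rule does no harm in Stage 1, where dose groups are filled in sequence and open label. In Stage 2 it replaces the random draw. The people who recruit and enrol know the arm of the subject who was never dosed, and the rule passes that arm to the replacement. Whoever selects the replacement could therefore, even without intending to, match a candidate to a known arm, for example on abdominal fat thickness, which is closely tied to a volume-loss endpoint.

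Because only subjects are blinded, an unpredictable allocation is one of the few protections left for the comparison of CBL-514 with placebo. The optional rule raises a related question: an unblinded Sponsor may decide which early stoppers to replace, with no criteria and no stated method of allocation.

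**Working it through.** **1. The plan's own figures.** Protocol 10.4.1 and Table S3 give 50 + 25 = 75 randomised, drop-out of 16% and 44%, and 56 evaluable.

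- Forward: 50 × (1 − 0.16) = 42; 25 × (1 − 0.44) = 14; 42 + 14 = 56.
- Backward: 42 / 0.84 = 50; 14 / 0.56 = 25; 50 + 25 = 75.

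The figures reproduce. The 75 already absorb the projected drop-out, so the plan's evaluable number does not depend on replacing dosed subjects. No alpha, power or responder rate is stated, so there is no power calculation for this point to alter.

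**2. Can the mandatory rule be triggered in Stage 2?** Yes. Randomisation comes before dosing on Day 1. Protocol 8.1 also has the Investigator judge before administration whether the minimum dose can be given, and Protocol 9.6 lists a Day 1 efficacy-related major violation as a Stage 2 withdrawal criterion. The text does not say that these judgements are complete before randomisation.

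**3. Is the replacement's arm random?** Not under 9.5. Read beside 10.3.2, the two sections cannot both hold for this subject. Section 9.6, which follows directly, sets out Stage 1 and Stage 2 criteria separately; 9.5 does not.

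**4. Is the arm knowable?** Section 10.7 lets the Investigator, site staff and Sponsor know the arm of the subject being replaced, and 9.5 transfers it. That the next enrollee's arm can be known in advance is an inference from these two sections, not a statement in either.

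**5. Effect on ITT counts.** With k never-dosed subjects, each replaced, the SAP definition gives N = 75 + k (76 for k = 1, 78 for k = 3), while the Protocol definition stays at 75.

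**6. Size for never-dosed cases.** The documents give no expected number, so k = 1 to 3 in an arm is an assumption. The largest possible shift in an arm's responder proportion is k divided by the planned arm size.

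| k | Placebo, k/25 | CBL-514, k/50 |
|---|---|---|
| 1 | 4 points | 2 points |
| 2 | 8 points | 4 points |
| 3 | 12 points | 6 points |

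These are limits, not expected bias. If only the 14 planned evaluable placebo subjects contribute, one subject is 1/14 = 7 points.

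**7. Assumed upper limit including drop-outs.** Projected drop-outs are 50 × 0.16 = 8 and 25 × 0.44 = 11, total 19. If all were replaced in the same arm, replacements would be 19/(75 + 19) = 19/94 = 20% overall, 11/(25 + 11) = 11/36 = 31% of placebo and 8/(50 + 8) = 8/58 = 14% of CBL-514. This requires that every drop-out occurs before dosing is complete, that the Sponsor replaces every one, and that each replacement takes the same arm. The documents state none of these.

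**The case against.** The strongest reply is that the problem is narrow. The same-treatment clause reaches only subjects who received no product, and the interval between randomisation and dosing on Day 1 is short. Stage 2 is descriptive (Protocol 16), and SAP 10 disclaims any claim based on its p-values. Much of this stands, and it limits the size of the point. It does not remove it: Protocol 13.3 still intends to judge the difference from placebo, SAP 10 estimates that difference at Visits 6 and 7, and selection bias distorts an estimate whether or not a formal test is declared.

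A reader might infer four stronger things that the documents do not support.

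- **That every Stage 2 replacement has a pre-set arm.** For subjects who stop during dosing the arm is simply not stated.
- **That 20% of Stage 2, or 31% of placebo, would be non-randomised.** Those figures rest on the assumptions in step 7. Some drop-outs may occur in follow-up, after dosing is complete (Stage 2 withdrawal criteria 3 and 6 in Protocol 9.6), where 9.5 does not apply. Replacing all 19 would also allow for the same attrition twice.
- **That the Sponsor chooses replacements after seeing individual response.** Section 10.7 establishes knowledge of the arm. No section says that ultrasound results are consulted when replacement is decided. A replaced subject who was dosed also remains in ITT.
- **That sites know who the next replacement will be.** No section says how or when an enrollee is designated a replacement.

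It is also fair to object that the next unused number could be visible to a Sponsor that runs the randomisation. That objection stands, and the fix therefore needs a concealment clause.

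**Conclusion.** The point holds in a limited form. As written, Protocol 9.5 fixes the arm of a Stage 2 replacement for a randomised, never-dosed subject, contradicts 10.3.2, and feeds that subject into ITT without distinction. The arm can be known before enrolment, given that staff are unblinded and no concealment step is described. The optional rule for subjects who stop during dosing is under-specified; it has not been shown to be non-random.

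Few never-dosed cases are expected. Each is worth at most 4 points of the placebo proportion or 2 points of the CBL-514 proportion on the planned arm sizes of 25 and 50. The 20% and 31% figures are only an assumed ceiling. This is a cheap improvement to the plan. It is not evidence that the Stage 2 comparison is biased, and it does not change the sample size.

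**What to change.** Amend Protocol 9.5 as follows, and reconcile it with 10.3.2.

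1. Limit the same-treatment rule to Stage 1.
2. In Stage 2, give any additional subject the next unused number on the randomisation schedule, whichever arm it carries, and keep upcoming assignments concealed from those who enrol.
3. State that any replacement of a dosed subject follows the same rule and is not chosen by arm or response. A complete ban on replacing dosed subjects is a design choice and is not needed here, although the 75 already allow for 16% and 44% drop-out.
4. Flag replacements in the ITT listing. If Stage 2 enrolment is already complete, report their number by arm and add a sensitivity analysis without them.
5. Align the Protocol and SAP definitions of ITT, so that it is clear whether a never-dosed subject and the replacement both count.

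The cost is one protocol paragraph and a listing flag. The final allocation may drift slightly from 2:1; the ratio would still hold in expectation.

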9.6. Subject Withdrawal Criteria

In accordance with applicable regulations, a subject has the right to withdraw from the study, at any time and for any reason, without prejudice to his (or her) future medical care. If a subject withdraws consent, the date and reason for consent withdrawal should be documented. Subject data will be included in the analysis up to the date of the withdrawal of consent.

A subject must be removed from the study at any time, if any of the following criteria are met:

Stage 1

1. Subject withdraws consent.
2. Between Screening and Day 1, subjects whose overall body weight change of ≥ 3 kg.
3. Subject has body weight change ≥ 5 % based on Day 1 body weight.
4. Any other clinical AE, medical condition, or situation that in the opinion of the Investigator would not be in the best interest of the subject.
5. Subject who cannot complete follow-up visits within 6 weeks post treatment visit.

Stage 2

1. Subject withdraws consent.
2. Subject has body weight change ≥ 3 kg compared to Day 1 body weight during the whole study period.
3. Subject has body weight change ≥ 3 kg during the follow-up period compared to the body weight from the last treatment visit.

4. Any other clinical AE, medical condition, or situation that in the opinion of the Investigator would not be in the best interest of the subject.
5. Subjects has a treatment interval > 6 weeks in length between any of the dosing courses.
6. Subject cannot complete at least the first follow-up visit (Visit 6 / EOT) within 6 weeks post final treatment visit, or cannot complete the second follow-up visit (Visit 7 / EOS) within 10 weeks post final treatment visit.
7. Subject has efficacy related major protocol violation at Day 1 (baseline)

If a subject is withdrawn because of an AE, the Investigator must arrange for the subject to have appropriate follow-up care until the AE is resolved or has stabilized. Unresolved AEs will be followed until the EOS/ET visit or until the Investigator and MM determine that further follow-up is no longer indicated.

If a subject asks or decides to withdraw from the study, the final ET evaluations (as per the schedule of study assessments) will be performed as completely as possible, all efforts will be made to complete and report the observations, especially the listed primary and secondary objectives, as thoroughly as possible up to the date of withdrawal. A clear and concise reason for withdrawal will be identified and recorded on the appropriate eCRF, along with the date of withdrawal.

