Subjects should have sufficient subcutaneous fat on their abdomen to receive injections on Day 1. This will be based on eligibility criteria set out in [inclusion criterion 3](#). Before administration, the Investigator should evaluate whether a subject is able to receive the minimum dose, 300 mg (25 injections) as defined by Study Drug Administration Manual. [REDACTED]

[REDACTED] If a subject is not able to receive the minimum injection dose, the ongoing treatment and post-dose assessments will be cancelled and the remaining treatment visits would not be required for that subject. For subjects that do not complete 4 treatments due to not enough residual fat, the subject will be requested to continue with follow-up visits (Visit 6 and 7). This arrangement would not be regarded as missing protocol required visits, or as discontinuation from the study.

If a subject cannot complete the 4 treatments and withdraws from the study because of reasons except for dose adjustment, only the ET visit should be performed for final follow-up.

Subjects will be screened for inclusion and exclusion criteria during a 28-day screening period (Day -28 to Day -1). At Visit 2 (Day 1), eligible subjects will be randomized 2:1: (i.e., CBL-514 group: 50 subjects; placebo group: 25 subjects) to receive CBL-514 or placebo, respectively.

Subjects will visit the site on each of the study visits and will remain onsite for observation for 1 hour after the administration of the IP, or shorter/ longer at the discretion of the Investigator and until all planned assessments for the visit are completed.

An ET visit has been planned for subjects who are withdrawn from the study earlier than planned for assessment as soon as possible after early withdrawal, no later than 6 weeks from the last dose received.

A subject diary will be provided to each subject to record if there are any changes to the injection site/s or any discomforts in between visits. Subjects will be instructed to bring the subject diary with them for all visits to the clinic.

Study visits and assessments for Stage 2 of the study will occur as delineated in the Schedule of Assessments presented in [Table 5](#).

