AE: Adverse event; AESI: Adverse event of special interest; Ag/Ab: Antigen/antibody; ALP/ALKP: Alkaline phosphatase; ALT: Alanine aminotransferase; aPTT: Activated partial thromboplastin time; AST: aspartate aminotransferase; β-hCG: Beta human chorionic gonadotropin; BMI: Body mass index; ECG: Electrocardiogram; eGFR: Estimated glomerular filtration rate; EOT: End of treatment; EOS: End of study; ET: Early Termination; FBS: Fasting blood sugar; FSH: Follicle stimulating hormone; GGT: Gamma-glutamyl transferase; Hb: Hemoglobin; HbA1c: Hemoglobin A1c; HBV: Hepatitis B Virus; Hct: Hematocrit; HCV: Hepatitis C Virus; HDL-C: High-density lipoprotein cholesterol; HIV: Human immunodeficiency virus; INR: International normalized ratio; ISR: Injection site reaction; LDL-C: Low-density lipoprotein cholesterol; RBC: Red blood cell; SAE: Serious adverse event; TBIL: Total bilirubin; WBC: White blood cell; WOCBP: Woman of childbearing potential.

- * Available measurements of clinical evaluations (physical examinations, vital signs, and ECG) and laboratory evaluations (biochemistry, hematology, coagulation, and urinalysis) within 14 days prior to CBL-514 or Placebo dose can be accepted as the Baseline value and will not necessitate duplicate examinations.
- * If study drug dose is within 7 days of Screening pregnancy test, pregnancy test at Visit 2 (Day 1) will not be necessary to assess.
- * In cases where more than 1 data is available for a certain evaluation, the latest value prior to the study drug administration will be used as the Baseline value.

- ** The first follow up visit (Visit 6) should be performed 4 weeks post the final treatment. If treatment is cancelled at Visits 3, 4 or 5 due to the insufficient abdominal fat, it is recommended that first follow up visit is performed on the same day of the treatment cancellation. If not, then +7 days visit window should be utilized to schedule another day to complete the first follow up visit.
- ¹ Details of concurrent medical conditions, prior surgical procedures and chronic diseases or other significant medical events prior to Screening will be collected. Any other non-significant medical events within 6 months prior to Screening will also be collected. Prior medications include a complete history of previous treatment/medications within 6 months prior to Screening.

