12.2.5. Visit 7: End of Study Visit (Visit 5+ 8 weeks [±7 Days])

Subjects will return to the study site for an EOS assessment 8 weeks after Visit 5 with a visit window of ±7 days.

The following assessments will be carried out unless otherwise noted:

- Review Subject diary
- Collect anthropometric parameters (including body weight)
- Perform abdominal ultrasound. Abdominal ultrasound may be performed up to 4 days before/after Visit 7
- Perform medical examinations:
 - Perform physical examination⁸
 - Perform injection site assessment
- Take photographs on the target abdominal area
- Review and record AEs
- Review and record subject's concomitant medications with the reason for administration, only if a medication is related to AEs following the Visit 6.

This visit marks the end of participation in this study.

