12.2.6. Early Termination (if applicable)

Subjects who withdraw early from the study will be asked to return to the study site for an EOS assessment at ET visit as soon as possible after withdrawal, no later than 6 weeks from the last dose received.

The following procedures will be conducted:

- Review Subject diary
- Collect anthropometric parameters (including body weight)
- Perform abdominal ultrasound. Abdominal ultrasound may be performed up to 4 days before/after ET Visit

⁸ Assessment/collection can be performed on or within 4-days window prior to visit date.

- Satisfaction Questionnaire will be dispensed, and subjects should complete the Questionnaire at this visit. Site will review and record the Questionnaire
- Perform medical examinations:
 - Physical examination⁹
 - Injection site assessment
 - Vital signs (body temperature, pulse rate, systolic and diastolic BP, and respiratory rate) evaluation⁹
 - ECG¹⁰
- Collect blood/urine to perform laboratory evaluations⁹:
 - Biochemistry panel
 - Hematology panel
 - Coagulation panel
 - Urinalysis
 - Pregnancy test for WOCBP (urine)
- Take photographs on the target abdominal area
- Review and record AEs
- Review and record subject's concomitant medications with the reason for administration.

This visit marks the end of participation for subjects that withdraw early from the study.

⁹ Assessment/collection can be performed on or within 4-days window prior to visit date.

¹⁰ ECG assessment can be performed on or within 4 days before or after visit date.

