16.1.1. Intent-to-treat Population

The ITT population will include all enrolled or randomized subjects who received at least one course of IP treatment.

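### A dosed Stage 2 subject removed under withdrawal criterion 7 before completing four treatments loses the Visit 7 primary outcome, although ITT keeps the subject and PP already excludes the violation

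*Protocol*

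**What the plan says.** **Removal.** The lead-in to Protocol 9.6 is mandatory and concerns the study, not only dosing: "A subject must be removed from the study at any time, if any of the following criteria are met". Stage 2 criterion 7 reads "Subject has efficacy related major protocol violation at Day 1 (baseline", and the synopsis repeats it. Stage 1 has no such criterion; there, the same kind of violation leads only to PP exclusion.

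**Follow-up after removal.** Under Protocol 8.1, a subject who withdraws before completing four treatments, for a reason other than dose adjustment, has a single remaining visit: "only the ET visit should be performed for final follow-up". Section 12.2.6 places it within 6 weeks of the last dose, includes an ultrasound, and adds: "This visit marks the end of participation for subjects that withdraw early from the study".

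**Existing alternative.** Section 8.1 treats subjects who stop dosing for lack of residual fat differently: "the subject will be requested to continue with follow-up visits (Visit 6 and 7".

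**Analysis.** The Stage 2 primary endpoint names Baseline, Visit 6 and Visit 7, and its analysis set is ITT. Protocol 16.1.1 defines that set: "The ITT population will include all enrolled or randomized subjects who received at least one course of IP treatment". SAP 4.1.1 includes everyone randomised, in the randomised arm. Stage 2 PP item 2, in both documents, excludes efficacy-related major violations. SAP 3.1 takes percentages over subjects with non-missing data, and SAP Addendum 1.0 removed imputation.

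**The concern.** Criterion 7 turns a protocol violation into missing outcome data. A violation is normally handled by excluding the subject from PP while follow-up continues for ITT. Here the plan keeps the subject in the primary population by name but stops collecting the outcome that population needs. Safety is not the reason, because criterion 4 covers removal for adverse events or medical conditions.

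Two features make the loss worth avoiding. The placebo arm is small: 25 randomised, 14 planned evaluable. And under Protocol 10.7 the Investigator, site staff, Sponsor and Medical Monitor all know the arm, so the judgement that a violation is major is not blinded. Stage 2 is exploratory with no formal testing, so the estimate is at stake, not an error rate.

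**Working it through.** **1. The plan's evaluable numbers.** Inputs: 50 and 25 randomised, drop-out 16% and 44% (synopsis, Protocol 10.4.1).

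- CBL-514: 50 × (1 − 0.16) = 42
- Placebo: 25 × (1 − 0.44) = 14
- Total: 42 + 14 = 56, as stated. The plan accepts 75 − 56 = 19 of 75 (25.3%) as non-evaluable and does not say how many of these come from criterion 7.

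**2. Can the ET visit stand in for Visit 7?** ET is due at the latest 6 × 7 = 42 days after the last dose. Visit 7 is "for an EOS assessment 8 weeks after Visit 5 with a visit window of" 7 days, so it opens at 8 × 7 − 7 = 49 days when Visit 5 is the final treatment. The visits do not overlap. With the 4-day scan allowances the extreme scan dates do (ET up to day 46, Visit 7 from day 45), but ET is to be held as soon as possible, shares a schedule column with Visit 6, and is nowhere mapped to Visit 7.

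**3. What happens to the subject in the analysis?**

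| Step | Source | Result for a dosed subject removed before four treatments |
|---|---|---|
| ITT | Protocol 16.1.1; SAP 4.1.1 | retained under both definitions |
| PP | SAP 4.1.4, item 2 | excluded by the violation itself |
| Visit 7 value | Protocol 8.1, 12.2.6 | not collected |
| Imputation | SAP Addendum 1.0 | none |
| Denominator | SAP 3.1 | non-missing only, so the subject leaves the Visit 7 proportion |

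The last row assumes the endpoint is read per visit; the documents do not say how Visits 6 and 7 combine. Protocol 16 uses the whole analysis set as denominator but lets the SAP prevail. On either denominator the actual outcome is unknown.

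**4. Can criterion 7 reach a subject already dosed?** An ineligibility recognised after dosing could. So could a dosing error if criterion 7 uses the list in Protocol 8.3 (wrong dose group; compliance outside 90% to 110% per treatment), which is an assumption. Example, taking the 25-injection minimum as the required amount: 22/25 = 88%, and 22 × 2.4 mL × 5 mg/mL = 264 mg against 300 mg.

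**5. Effect of one subject lost at Visit 7.** Responder shares are assumed: about 30% to 80% on CBL-514, one responder on placebo. Intervals are Clopper-Pearson 95%.

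| Arm | Responder lost | Non-responder lost |
|---|---|---|
| CBL-514, n=50 | 15/50 = 30.0% to 14/49 = 28.6% (−1.4) | 40/50 = 80.0% to 40/49 = 81.6% (+1.6) |
| CBL-514, n=42 | 13/42 = 31.0% to 12/41 = 29.3% (−1.7) | 34/42 = 81.0% to 34/41 = 82.9% (+2.0) |
| Placebo, n=25 | 1/25 = 4.0% (0.1–20.4) to 0/24 (0–14.2) (−4.0) | 1/25 to 1/24 = 4.2% (0.1–21.1) (+0.2) |
| Placebo, n=14 | 1/14 = 7.1% (0.2–33.9) to 0/13 (0–24.7) (−7.1) | 1/14 to 1/13 = 7.7% (0.2–36.0) (+0.5) |

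The n=42 and n=14 rows may count a loss twice, because those figures are already net of planned drop-out. Adding one retained subject to 14 avoids this: 1/14 = 7.1% becomes 1/15 = 6.7% or 2/15 = 13.3%.

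**The case against.** **The trigger may be narrower.** Criterion 7 could mean only a spoiled baseline, such as an unusable scan; a subject without a valid baseline loses nothing usable. The definitions sit in the Protocol Deviation Management Plan cited in SAP 6, which is not available. This stands as a limit on frequency. It does not remove the case, since an eligibility or dosing violation recognised after the first injection can coexist with a valid baseline scan. The compliance example is also narrow: Investigator dose adjustment is exempt, and a subject judged before dosing unable to receive the minimum keeps Visits 6 and 7.

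**Some losses are mitigated.** Protocol 9.5 allows replacement, and the MMRM for fat volume uses scans from Visit 3 onward. Both are true, but neither recovers the removed subject's Visit 7 responder status. A violation found before dosing, or classified only after Visit 7 (SAP 6 allows review up to database lock), costs nothing.

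**Other criteria lose data the same way.** Weight change and a long dosing interval are also mandatory removals that can lead to ET only. That is correct; this point does not repair them, though reporting missing values would show them.

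**Stronger readings to avoid.** A reader might infer that unblinded staff could use the rule to favour CBL-514. The documents do not support that: the criterion is mandatory, and any bias depends on the violation and on who is lost. A reader might also infer that every ET scan should be analysed as Visit 6, given the shared column and the absence of visit windows in SAP 3.1. That goes too far. ET follows withdrawal as soon as possible and could fall days after a single treatment, whereas for Visit 6: "The first follow up visit (Visit 6) should be performed 4 weeks post the final treatment". SAP 10 also limits tables to scheduled visits. Treating any ET scan as Visit 6 would be a form of carry-forward.

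**Conclusion.** The point holds in a limited form. For a randomised, dosed Stage 2 subject with a valid baseline scan who is removed under criterion 7 before completing four treatments, the Visit 7 primary outcome is lost under the protocol's own rules, with no gain for ITT or PP.

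The number affected is unknown and probably small, and the planned drop-out may already include it. One lost subject shifts a Visit 7 proportion by up to about 2 points on CBL-514. On placebo the largest shift is 4.0 points at n=25, and 7.1 points at n=14 with the double-counting caveat. These shifts rest on the assumed responder shares and a per-visit reading of the endpoint. They are small beside the placebo confidence intervals. This is a cheap improvement to the plan, not a threat to the study's conclusions.

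**What to change.** **Protocol 9.6 and synopsis.** Reword criterion 7 so that a Day 1 efficacy-related major violation stops further dosing only where that is needed and leads to exclusion from PP, not removal from the study.

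**Follow-up.** Every randomised, dosed subject with a valid baseline scan attends Visits 6 and 7 and is analysed in ITT in the randomised arm. If dosing stops, use the path section 8.1 already gives for too little residual fat, with the visits 4 and 8 weeks after the subject's final treatment. If dosing continues, keep the normal schedule.

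**SAP 10.** Report, per arm, how many ITT subjects lack a Visit 6 value and how many lack a Visit 7 value. Do not add a rule that counts every ET scan as Visit 6 regardless of timing. If follow-up is already complete, this reporting can still be added.

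**Cost.** A small amendment with sign-off and IRB/IEC submission under Protocol 22.1, and a sentence in the SAP. Each affected subject keeps up to two visits that were already scheduled, with no new procedure. The ITT estimate may be slightly diluted by subjects who were ineligible or wrongly dosed; the PP analysis still excludes them.
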